6.1.5.2 Tapering Guidelines

Tapering of corticosteroids, CNI, and ruxolitinib will follow 2 steps: first taper systemic corticosteroids following documented CR or PR, and follow with taper of CNI/ruxolitinib.

The taper of corticosteroids, in responding subjects (CR or PR) as outlined in [Table 6-2](#), must not be attempted earlier than approximately 2 weeks from the time of documented CR or PR. In responding subjects, the taper of ruxolitinib must not be attempted until the subject is off corticosteroids and CNIs AND the subject has completed the assessments for Cycle 7 Day 1.

During the Treatment Period, immunosuppression taper guidelines are:

- **Corticosteroids:** Every effort should be made to use the minimum dose of corticosteroid that is sufficient to control cGvHD manifestation. It is recommended that a taper of corticosteroids should be attempted approximately two weeks after achieving a documented CR or PR. Guidelines are included in [Table 6-2](#). If a flare should occur during the taper, the treatment should continue for at least 3 months prior to attempting to resume the taper.

Table 6-2 Corticosteroid taper guidelines

Week (time from achieving a CR or PR)	Dose, mg/kg body weight
0	Current dose of corticosteroid every (Q) day (example 1 mg)
2	Current dose of corticosteroid (1 mg)/ decrease alternate day dose by 50%* (0.5 mg)
4	Current dose of corticosteroid (1 mg)/decrease alternate day dose by 50%* (0.25 mg)
6	Current dose of corticosteroid every other day (QOD): 1 mg every other day
8	Decrease current dose of corticosteroid by 10% every 2 weeks until off

*Alternate-day administration
([Flowers and Martin, 2015](#))

- **CNI (cyclosporine or tacrolimus):** Once off systemic corticosteroids, and documented CR or PR, starting at Cycle 7 Day 1 at 25% dose reduction per month is allowed, or to be tapered per institutional practice.

- **Ruxolitinib:** Once off systemic corticosteroids, ruxolitinib taper is allowed in subjects demonstrating a CR or PR, starting no earlier than Cycle 7 Day 1. The following guidance may be followed based on evaluation of patient condition, current dosing regimen and the clinical judgement of Investigator: a 50% dose reduction every 2 months (approximately 56 days) can be initiated. If sustained cGvHD response is observed (i.e. no worsening of cGvHD signs and symptoms), subject can be further tapered by a second 50% dosage reduction based on investigator assessment and judgement.

6.1.5.2.1 cGvHD Flare

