6.2 Other treatment(s)

6.2.1 Concomitant Medications

All medications, procedures and significant non-drug therapies (including physical therapy and blood transfusions) administered after the subject was enrolled into the study must be recorded on the appropriate eCRF.

Each concomitant drug must be individually assessed against all exclusion criteria/prohibited medication. If in doubt the investigator should contact the Novartis medical monitor before enrolling a subject or allowing a new medication to be started. If the subject is already enrolled, contact Novartis to determine if the subject should continue participation in the study.

Supportive treatments per institutional guidelines for management of alloSCT subjects with cGvHD or SR-cGvHD are allowed. The subject must be told to notify the investigational site about any new medications he/she takes after the start of treatment.

All medications (other than ruxolitinib and systemic corticosteroids) including over-the-counter medications and vitamins must be listed on the Concomitant Medications electronic case report

form (eCRF). Refer to [Section 6.2.2](#) for a list of prohibited concomitant medications during study treatment. Significant non-drug therapies (including physical therapy and blood transfusions) administered during the study must be listed on the significant non-drug therapies eCRF. Steroid usage in the 18 months prior to the first dose of ruxolitinib and any other prior medication received up to 30 days prior to the first dose of ruxolitinib must be recorded on the appropriate eCRF. Subjects will be instructed not to take any additional medications (including over-the-counter products) during the course of the study without consultation with the Investigator.

In addition to assigned ruxolitinib, subjects may receive standard alloSCT supportive care including anti-infective medications and transfusion support.

Use of CNIs (cyclosporine or tacrolimus) if initiated at least 3 weeks prior to the start of ruxolitinib (Cycle 1 Day 1), and topical corticosteroid therapy per institutional guidelines is permitted and must be listed on the corresponding concomitant medications eCRF.

Permitted concomitant medications are described in [Section 6.2.1.1](#).

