12.4.1 Definition of primary endpoint(s)

The primary efficacy variable of the study is **overall response rate (ORR)** at Cycle 7 Day 1, defined as the proportion of subjects demonstrating a complete response (CR) or partial response (PR), according to the NIH Consensus Criteria ([Lee et al 2015](#)). Note that response is relative to the assessment of cGvHD at baseline.

- **Complete response** is defined as complete resolution of all signs and symptoms of cGvHD in all evaluable organs without initiation of any new systemic therapy.
- **Partial response** is defined as an improvement in at least one organ (e.g. improvement of 1 or more points on a 4 to 7 point scale, or an improvement of 2 or more points on a 10 to 12 point scale) without progression in other organs or sites, or initiation/ addition of new systemic therapies.
- **Lack of response** is defined as unchanged, mixed response, or progression. (Please refer to [Table 8-3](#) and [Table 16-3](#) for the definitions of "unchanged", "mixed response" and "progression".)

cGvHD Flare and **cGvHD Recurrence** are not considered as a treatment failure, unless they require a change or addition of another systemic treatment defined as below.

- **cGvHD Flare** is defined as any increase in symptoms or therapy for cGvHD after an initial response (CR or PR). A cGvHD flare is not considered a treatment failure unless a change or addition of another systemic treatment, including CNIs, occurs.
- **cGvHD Recurrence** is defined as the return of cGvHD disease after tapering off study treatment due to response. Following completion of a taper of systemic therapy, if worsening of cGvHD symptoms occur, the patient is allowed to resume treatment for cGvHD as per local institutional practice. For the statistical analyses, re-start of treatment for cGvHD is handled in the same way as addition or initiation of new systemic treatment.

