16.4.3 Efficacy Assessments - Overall response assessment at one time point

Following the NIH working group recommendations the overall response evaluation (at each scheduled post-baseline time point/assessment) will be based on the evaluations for skin, eyes, mouth, esophagus, upper GI, lower GI, liver, lungs and joints/fascia. For each post-baseline assessment comparison will be made to baseline (C1D1).

- Complete response is defined as complete resolution of all signs and symptoms of cGvHD in all evaluable organs without addition of new systemic therapy, including CNIs.
- Partial response is defined as an improvement in at least one organ (e.g. improvement of 1 or more points on a 4 to 7 point scale, or an improvement of 2 or more points on a 10 to 12 point scale) without progression in other organs or sites, or initiation/addition of new systemic therapies.
- Lack of response is defined as unchanged, mixed response, or progression.
- Progression is defined as worsening of at least one organ and no improvement (CR or PR) in any other organ.
- Mixed response is a CR or PR in at least 1 organ accompanied by progression in another organ.
- Unchanged response is defined as stable disease or absence of improvement in any organ involved by cGvHD.

cGvHD Flare: is defined as any increase in symptoms or therapy for cGvHD after an initial response (CR or PR). A cGvHD flare is not considered a treatment failure unless a change of therapy or addition of another systemic treatment, including CNIs, occurs.

cGvHD Recurrence is defined as the return of cGvHD disease after tapering off study treatment due to response. Following completion of a taper of systemic therapy, if worsening of cGvHD symptoms occur, the patient is allowed to resume treatment for cGvHD as per local institutional practice. For the statistical analyses re-start of treatment for cGvHD is handled in the same way as addition or initiation of new systemic treatment.

Table 16-5 summarizes the rules for overall response assessment based on organ-specific evaluations at a scheduled post-baseline visit (e.g. the primary endpoint at Month 6 – Cycle 7 Day 1).

Table 16-5 Overall response evaluation

	Organ-specific response ¹				

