2.5.1 Primary endpoint

The primary efficacy variable of the study is **overall response rate (ORR)** at Cycle 7 Day 1, defined as the proportion of subjects demonstrating a complete response (CR) or partial response (PR), according to the NIH Consensus Criteria ([Lee et al 2015](#)) as reported in the CRF. Note that response is relative to the assessment of cGvHD at baseline.

- **Complete response** is defined as complete resolution of all signs and symptoms of cGvHD in all evaluable organs without initiation of any new systemic therapy.
- **Partial response** is defined as an improvement in at least one organ (e.g. improvement of 1 or more points on a 4 to 7 point scale, or an improvement of 2 or more points on a 10 to 12 point scale) without progression in other organs or sites, or initiation/ addition of new systemic therapies.
- **Lack of response** is defined as unchanged, mixed response, or progression. (Please refer to Table 8-3 and Table 16-3 in the protocol for the definitions of "unchanged", "mixed response" and "progression".)

cGvHD Flare and **cGvHD Recurrence** are not considered as a treatment failure, unless they require a change or addition of another systemic treatment defined as below.

- **cGvHD Flare** is defined as any increase in symptoms or therapy for cGvHD after an initial response (CR or PR). A cGvHD flare is not considered a treatment failure unless a change or addition of another systemic treatment, including CNIs, occurs.
- **cGvHD Recurrence** is defined as the return of cGvHD disease after tapering off study treatment due to response. Following completion of a taper of systemic therapy, if worsening of cGvHD symptoms occur, the patient is allowed to resume treatment for cGvHD as per local institutional practice. For the statistical analyses, re-start of treatment for cGvHD is handled in the same way as addition or initiation of new systemic treatment.

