5.4.3 Definition of new or additional systemic treatment of cGvHD

The data source to search for the new or additional systemic therapy would be from eCRFs of “Prior and Concomitant Medication” (CONMED) or eCRFs “Prior or Concomitant non-drug therapies/procedures”.

Systemic therapies are identified using the Route (if CMROUTE is Intramuscular, Intravenous, Oral, Subcutaneous, or Parenteral). Therapies with CMROUTE = ‘ORAL’ will be considered as systemic only if in addition CMADMIN = “SYSTEMIC”.

Any of the following therapies represent new or additional systemic therapy for cGvHD:

- Any CNI therapy being initiated newly as ‘treatment for cGvHD’ or ‘treatment for SR-cGvHD’ after the baseline (as recorded on CONMED). That means when a subject starts a new systemic therapy during study treatment for the indication ‘treatment for cGvHD’ or ‘treatment for SR-cGvHD’, or a subject received the same therapy before as prophylaxis and then changed to treatment of cGvHD/SR-cGvHD as indication, this will be considered as new or additional systemic treatment.

CNI therapy given as ‘treatment for cGvHD’ or ‘treatment for SR-cGvHD’ that started after Cycle 1 Day 1 will be considered as new or additional systemic treatment, even if the same therapy was given as treatment for (SR-) cGvHD already before start of study treatment but the patient was not receiving such therapy on Cycle 1 Day 1. Whereas a stop of such therapy after Cycle 1 Day 1 and later re-start of the same therapy will not be considered as new or additional therapy.

Change of the drug within the defined group of CNIs or only change of the dose is not considered as new CNI treatment.

- Any other systemic treatments (excluding CNI and steroids) being initiated newly as ‘treatment for cGvHD’ or ‘treatment for SR-cGvHD’ after the baseline and documented in CONMED (according to the same definitions as for CNI treatments above).
- Any other non-drug therapy/procedure being initiated newly as ‘treatment for cGvHD’ or ‘treatment for SR-cGvHD’ after the baseline (according to the same definitions as for CNI above) and documented on concomitant non-drug therapies/procedures (e.g. ECP).

Changes in the systemic corticosteroid therapy (captured on study treatment eCRF), e.g. change of the drug, the dose or any interruption and re-start, will not be taken into account for identification of new or additional systemic therapy, nor will any other corticosteroid therapy (in CONMED) be considered.

6 Reference

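### SAP 5.4.3 does not carry out the plan's own rule that re-starting cGvHD treatment after a recurrence counts as new systemic therapy

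*SAP*

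**What the plan says.** **The rule.** SAP 2.5.1 defines recurrence as return of cGvHD after study treatment was tapered off for response, and adds: "For the statistical analyses, re-start of treatment for cGvHD is handled in the same way as addition or initiation of new systemic treatment". Protocol 12.4.1 ("re-start of treatment for cGvHD is handled in the same way as addition or initiation of new systemic treatment") and protocol 16.4.3 ("For the statistical analyses re-start of treatment for cGvHD is handled in the same way as addition or initiation of new systemic treatment") agree.

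**The implementation.** SAP 2.4.2.4 refers to SAP 5.4.3 for the detailed specification, which reads as follows.

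- Source: "The data source to search for the new or additional systemic therapy would be from eCRFs of" the prior and concomitant medication pages, or the non-drug therapy and procedure pages.
- CNI: "stop of such therapy after Cycle 1 Day 1 and later re-start of the same therapy will not be considered as new or additional". Other systemic drugs and procedures follow the same definitions.
- Corticosteroids: "Changes in the systemic corticosteroid therapy (captured on study treatment eCRF), e.g. change of the drug, the dose or any interruption and re-start" are not taken into account, nor is any corticosteroid on the concomitant medication page.

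**Where ruxolitinib is recorded.** Protocol 6.2.1: "All medications (other than ruxolitinib and systemic corticosteroids) including over-the-counter medications and vitamins must be listed on the Concomitant Medications" form. SAP 2.1.1 and 2.4.1 store the gap of a subject who tapers off and re-starts as a dose interruption on the exposure record.

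**Where the definition is used.** New systemic therapy is component iii of FFS and an event for DOR (SAP 2.7.1). Under SAP 2.13, new systemic therapy after flare or recurrence, at any time, makes the subject a non-responder for corticosteroid-free response. All three are in the final CSR (SAP Table 1-1).

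**The concern.** The plan states a rule for re-start after recurrence and then gives the programmer a definition with no step that applies it. The FFS and DOR sections do not say which text governs, no order of precedence is given, and SAP Section 4 lists only an added exploratory endpoint, so no departure from the protocol is declared.

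The case is foreseen. Protocol 6.1.5 allows ruxolitinib to be re-initiated after recurrence. The October 2024 SAP added rules for exposure, dose intensity and the on-treatment period for subjects who re-start, but no efficacy rule for them in 5.4.3.

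Each missed re-start removes a failure, so the error runs one way. Recurrence is not itself an FFS event; it can enter only through component iii. DOR also counts progression, but progression is judged against Cycle 1 Day 1, so a milder recurrence escapes there too. With fewer than 5 recurrences after taper-off, SAP 2.13 gives only a listing, and no time-to-recurrence estimate would show them.

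**Working it through.** **Step 1. Follow each re-start route through 5.4.3** for a subject tapered off for response who then recurs.

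| Therapy re-started | SAP 2.5.1, protocol 12.4.1 and 16.4.3 | SAP 5.4.3 as written |
|---|---|---|
| Ruxolitinib | counts | not found: page not searched |
| Systemic corticosteroid | counts | excluded |
| Same CNI, stopped after Cycle 1 Day 1 | counts | excluded |
| Same other drug or procedure | counts | excluded, by reference to the CNI rule |
| New agent, or CNI not being taken on Cycle 1 Day 1 | counts | counts |

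The first four rows disagree, and 5.4.3 has no exception for re-start after a completed taper.

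**Step 2. Which endpoints can be affected.** Protocol 6.1.5.2 says that "the taper of ruxolitinib must not be attempted until the subject is off corticosteroids and CNIs AND the subject has completed the assessments"; the visit meant is Cycle 7 Day 1. Recurrence after tapering off study treatment therefore comes after the primary assessment, and ORR is essentially unaffected. BOR is too, because the response came before the taper. FFS, DOR (post-taper assessments are in scope for the additional DOR analysis in SAP 2.7.1) and corticosteroid-free response remain.

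**Step 3. Inputs.** Enrolled N = 46 (protocol, Amendment 2), assumed all in the FAS. SAP Table 3-1 gives a minimum of 30 responders for N = 46 and a probability of 0.809. This reproduces: 30 is the smallest count whose exact 90% lower limit reaches 0.50 (0.521), and P(X ≥ 30) for a binomial with n = 46 and p = 0.70 is 0.809. The number of affected subjects, k, is not in the documents. I show k = 1 to 4, since 4 is the most for which SAP 2.13 gives only a listing.

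**Step 4. Corticosteroid-free response.** Shift = k/46: 2.2, 4.3, 6.5 and 8.7 points for k = 1, 2, 3 and 4.

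**Step 5. FFS at 24 months.** Assume the re-start is at month 20 and the subject would otherwise be censored at month 36. The Kaplan-Meier drop is k × S(just before month 20) / number at risk. The counts of other events (10 or 18) and of earlier censorings (0, 6 or 12, spread evenly among the events) are assumptions.

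| Other events | Censored earlier | S before month 20 | At risk | Drop, k = 1 |
|---|---|---|---|---|
| 10 | 0 | 36/46 = 0.783 | 36 | 2.2 points (to 0.761) |
| 18 | 0 | 28/46 = 0.609 | 28 | 2.2 points (to 0.587) |
| 10 | 6 | 0.767 | 30 | 2.6 points |
| 18 | 6 | 0.578 | 22 | 2.6 points |
| 10 | 12 | 0.747 | 24 | 3.1 points |
| 18 | 12 | 0.537 | 16 | 3.4 points |

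For k = 4 the drop is four times as large: 8.7 points without earlier censoring, 10.2 to 10.5 with 6 censored, and roughly 12 to 13 with 12 censored.

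**Step 6. DOR.** With 30 responders, 1/30 = 3.3 points per subject before censoring. With 0.70 × 46 = 32.2, taken as 32, it is 1/32 = 3.1 points.

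**Step 7. Scale.** The 95% half-width for a proportion of 0.761 with n = 46 is 1.96 × √(0.761 × 0.239 / 46) = 0.123, about 12 points.

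**The case against.** - **The two texts may be cumulative.** 5.4.3 could define what is new, with 2.5.1 adding re-start as a special case. This reading is possible, but 5.4.3 does not refer to it, and a programmer following 5.4.3 would not implement it. The plan still needs a sentence.
- **FFS speaks of another therapy, and the re-start rule stands in the response sections.** Re-starting the same drug is arguably not another therapy. But the rule is worded for the statistical analyses in general and equates re-start with initiation. Confined to ORR at Cycle 7 Day 1 it would have almost nothing to do, because ruxolitinib taper begins only then. At best the point is unsettled.
- **Steroid re-escalation for a flare is not failure.** Correct: protocol 6.1.5.2.1 says so for flares during taper, and there 5.4.3 is consistent with it. The concern covers only re-start after full taper-off for response.
- **A ruxolitinib taper may not show that CNI is off.** Protocol 6.1.5.2 is inconsistent here: one sentence requires CNI to be off first, while others describe a joint CNI/ruxolitinib step and ask only that corticosteroids be off. Those passages must be reconciled. The finding survives, because recurrence is defined by tapering off study treatment, which is ruxolitinib plus corticosteroids.
- **Corticosteroid-free response at any time point** (protocol Table 2-1, SAP Table 1-1) would not be undone by a later re-start. This stands as a limit: the effect on that endpoint comes from the stricter sentence in SAP 2.13, which itself names recurrence.
- **The magnitudes are assumed.** They are. Also, DOR is based on best-response responders, a group at least as large as the ORR responders, so at a given ORR responder count the DOR figures per subject are upper values before censoring.
- **The route is narrow.** New agents are already caught, DOR has progression as a partial safeguard, and the endpoints carry no hypothesis tests.

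**Conclusion.** The concern holds. The protocol, in two places, and SAP 2.5.1 count re-start after recurrence in a tapered-off responder as new systemic therapy. SAP 5.4.3 excludes it or cannot find it whenever the re-started therapy is one the subject already had. Applied as written, it biases FFS, DOR and corticosteroid-free response favourably and departs from the protocol without declaring it.

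The size depends on an unknown count. Per subject it is 2.2 points for corticosteroid-free response, 2.2 to 3.4 for 24-month FFS under the stated event and censoring assumptions, and about 3 for DOR. Against a half-width of about 12 points, one subject is a small shift; four (8.7 points or more for corticosteroid-free response and FFS) are not. The primary endpoint is essentially untouched, and the affected endpoints are secondary or exploratory. It should be fixed, but it does not threaten the trial's main result.

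**What to change.** State that SAP 2.5.1 takes precedence, and add to 5.4.3: for subjects tapered off ruxolitinib for response with documented cGvHD recurrence, re-start of ruxolitinib, systemic corticosteroid, CNI or other systemic cGvHD therapy counts as new systemic therapy on the re-start date. Apply this explicitly to FFS, DOR and corticosteroid-free response.

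- **Sources:** the study treatment pages as well as the concomitant medication and procedure pages, plus the record of new cGvHD treatment since discontinuation named in SAP Table 2-2.
- **Identifying subjects:** permanent-discontinuation reason *responder*, or interruption reason *dose tapering following response*. Both are needed, because the gap of a subject who re-starts ruxolitinib is stored as an interruption and the first reason alone may miss that subject.
- **Unchanged:** steroid or CNI changes before full taper-off, including flare management, stay as now handled.

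If the sponsor prefers the 5.4.3 rule, it should be declared in SAP Section 4 as a change from the protocol, with the three endpoints shown under both rules.

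The cost is a few sentences and one derived flag from data already collected. The three estimates may look slightly less favourable.

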6.1 Study treatment

Study treatment includes:

- **Investigational treatment:**
 - Refers to ruxolitinib (investigational drug)
- **Other study treatment:**
 - Refers to the concomitant use of corticosteroids to treat treatment-naive cGvHD or SR-cGvHD

Ruxolitinib will be administered as a 5 mg ruxolitinib tablet or as ruxolitinib oral pediatric formulation twice a day.

- **Treatment-naive cGvHD:** In addition to ruxolitinib, treatment must include methylprednisolone (or equivalent prednisone)
- **SR-cGvHD:** In addition to ruxolitinib, concomitant use of corticosteroids is required

In addition to study treatment, subjects may receive standard alloSCT supportive care including anti-infective medications and transfusion support. Systemic immunosuppressive medications used for the prophylaxis of cGvHD may be continued after Cycle 1 Day 1 if initiated prior to diagnosis of cGvHD, i.e., not used as therapy but as continuation of prophylaxis. Dose adjustments of immunosuppressive prophylactic drugs with therapeutic intent or addition of systemic immunosuppressive medications for treatment of cGvHD are not allowed. Systemic CNIs may be continued after Cycle 1 Day 1 if initiated at least 3 weeks prior to the start of ruxolitinib, i.e. at Cycle 1 Day 1. CNI should be used at standard dosing and adjusted to therapeutic trough levels. Continued use of topical corticosteroid therapy for cGvHD per institutional guidelines are permitted. For SR-cGvHD subjects, cessation of other systemic treatment for cGvHD other than corticosteroids +/- CNI will be required prior to ruxolitinib initiation. Permitted concomitant medications are described in [Section 6.2.1.1](#).

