2.5.2 Statistical hypothesis, model, and method of analysis

The response rates for ORR at Cycle 7 Day 1, will be estimated on the Full Analysis Set (FAS) for all the patients, when all subjects have completed 1 year of treatment or discontinued earlier. Confidence intervals of 90% will be calculated based on the exact method ([Clopper and Pearson 1934](#)) for binomial distribution. Summary statistics (frequencies and percentages) will be provided. It is not planned to test any specific hypotheses related to the efficacy endpoint(s), but to provide estimates of efficacy endpoints in the pediatric population.

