2.5.3 Handling of missing values/censoring/discontinuations

Patients with missing assessments that prevent the evaluation of the primary endpoint will be considered non-responders. This includes missing overall cGvHD response assessments at baseline and/or Cycle 7 Day 1. The time window for the Cycle 7 Day 1 visit is defined in [Table 2-1](#) above.

No data imputation will be applied. Patients who discontinue study treatment should return for the regular assessments indicated in Protocol Section 9.1. Addition or initiation of a new systemic therapy before Cycle 7 Day 1 will be considered a treatment failure, and patients will be counted as non-responder in the primary analysis.

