49	31	0.63	0.881	0.505	0.747
50	32	0.64	0.859	0.514	0.753

4 Change to protocol specified analyses

One exploratory analysis endpoints is added:

Chronic GvHD recurrence following completion of a taper of systemic therapy (see [Section 2.13](#)).

5 Appendix

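### SAP 2.5.1 and Protocol 12.4.1 and 16.4.3 can be read to make a switch of calcineurin inhibitor for a cGvHD flare a treatment failure, but the programmed definition in SAP 5.4.3 does not count it

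*SAP*

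**What the plan says.** The flare rule appears three times. SAP 2.5.1 states: "A cGvHD flare is not considered a treatment failure unless a change or addition of another systemic treatment, including CNIs, occurs". Protocol 12.4.1 has the same sentence. Protocol 16.4.3 is a little wider: "A cGvHD flare is not considered a treatment failure unless a change of therapy or addition of another systemic treatment, including CNIs, occurs".

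The rule that turns failure into non-response is narrower. SAP 2.5.3 says "Addition or initiation of a new systemic therapy before Cycle 7 Day 1 will be considered a treatment failure", and Protocol 12.4.3 matches it. Neither mentions a change of an existing treatment.

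SAP 5.4.3 defines the event for programming from the concomitant-medication and procedure records. For CNIs it says "Change of the drug within the defined group of CNIs or only change of the dose is not considered as new CNI treatment". It does count a child as having new treatment where "a subject received the same therapy before as prophylaxis and then changed to treatment of cGvHD/SR-cGvHD as indication".

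The situation can arise, because Protocol 6.1 says "Systemic CNIs may be continued after Cycle 1 Day 1 if initiated at least 3 weeks prior to the start of ruxolitinib", and Protocol 6.1.5.2 names two such drugs, cyclosporine and tacrolimus. SAP section 4, where departures from the protocol are declared, reports only that "One exploratory analysis endpoints is added".

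**The concern.** The flare sentences name both change and addition, and all three mention CNIs. The programmed definition leaves out a change between CNIs, whatever prompted it. A child who flares during the steroid taper, is moved from cyclosporine to tacrolimus because of the flare, and is in partial response against baseline at Cycle 7 Day 1 can therefore be a non-responder under one section of the SAP and a responder under another.

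The SAP itself treats CNIs as able to affect the outcome. Section 2.4.2.4 counts a CNI started during the study as new treatment even without lack of efficacy, because an effect on response cannot be ruled out. At stake is whether a response reached after a change in background immunosuppression is credited to ruxolitinib in the primary endpoint of a single-arm, open-label trial. Response at Cycle 4 Day 1 and best overall response rest on the same definition.

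**Working it through.** **1. The passages side by side**, for a switch between CNIs made because of a flare:

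| Place | What triggers failure | CNI switch for flare |
|---|---|---|
| SAP 2.5.1, Protocol 12.4.1 | change or addition, CNIs named | failure, on one reading |
| Protocol 16.4.3 | change of therapy or addition, CNIs named | failure, more directly |
| SAP 2.5.3, Protocol 12.4.3 | addition or initiation only | not mentioned |
| SAP 5.4.3 | newly started therapy; change within CNIs excluded | not a failure |

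**2. Direction.** Failures under the stricter reading are those that 5.4.3 flags plus the switches. So the response rate under 5.4.3 is at least as high as under the stricter reading, and never lower.

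**3. Who is affected.** Protocol 5.1 allows treatment-naive children no earlier systemic cGvHD treatment beyond 72 hours of corticosteroid, so a CNI they take at baseline should be prophylaxis. If its indication becomes treatment, 5.4.3 already counts it as new. What remains is mainly steroid-refractory children taking a CNI as treatment at Cycle 1 Day 1.

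**4. Which endpoints.** The two response rates at fixed visits are directly exposed. Best overall response shares the definition, but a flare by definition follows a response, so the earlier response would normally have been counted already. Failure-free survival and duration of response mention only added or started therapy, so the conflict over change does not arise in their wording.

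**5. The plan's own figures.** SAP 2.5.2 says "Confidence intervals of 90% will be calculated based on the exact method". For x responders of n, the lower limit is the 0.05 quantile of Beta(x, n−x+1) and the upper limit is the 0.95 quantile of Beta(x+1, n−x). The probability is P(X ≥ r) for X ~ Bin(n, 0.70), where r is the smallest count with a lower limit of at least 0.50.

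- n = 42: r = 27, limits 0.505 to 0.765, probability 0.836.
- n = 46: r = 30, limits 0.521 to 0.768, probability 0.809.

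Both rows agree with Protocol Table 12-1 and SAP Table 3-1. The planning figures are not in dispute.

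**6. Size per child.** Moving k children from responder to non-responder lowers the rate by k/n: 1/42 = 2.4 points, 1/46 = 2.2 points. For one child at the planning threshold:

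- 30/46 = 65.2%, lower limit 0.521; 29/46 = 63.0%, lower limit 0.499.
- 27/42 = 64.3%, lower limit 0.505; 26/42 = 61.9%, lower limit 0.480.

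If the planned 70% is taken to be counted under 5.4.3, reaching the target after one child is moved needs r + 1 counted responders. The probability goes from 0.836 to 0.743 at n = 42 and from 0.809 to 0.713 at n = 46.

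**7. How many children.** The documents give no figure for CNI use or switching. As an illustration only, assume that 10–36% of responders flare before Cycle 7 Day 1, 30–70% of those are on a CNI, 5–20% of those are switched, and 50–80% of those are in response at Cycle 7 Day 1:

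- Low: 46 × 0.70 × 0.10 × 0.30 × 0.05 × 0.50 = 0.02 children.
- High: 46 × 0.70 × 0.36 × 0.70 × 0.20 × 0.80 = 1.3 children (1.3/46 = 2.8 points).

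The high end is generous. The 36% is 13/36 relapses or progressions in an adult series reported with 24-month follow-up, and the product uses all 46 children, not only the steroid-refractory ones. If half are steroid-refractory (an assumption), the high end halves to 0.65.

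**The case against.** The strongest reply is that no passage says outright that a CNI-to-CNI switch is a failure. In SAP 2.5.1 and Protocol 12.4.1, the word for a different treatment may govern both change and addition, so that naming CNIs only tells the reader that adding one counts. Most of the plan is consistent with this. The primary endpoint, the definitions of complete and partial response, SAP 2.5.3, Protocol 12.4.3 and the flare paragraph in Protocol 6.1.5.2.1 all speak of added or newly started therapy. Protocol 16.4.3 cannot be taken literally either, since re-escalating corticosteroids is a change of therapy and Protocol 6.1.5.2.1 says that it is not a failure. The more detailed rules for identifying new therapy were added in the November 2022 SAP, before database lock, so 5.4.3 can be seen as the prespecified clarification.

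Much of this stands. A reader might infer that the plan clearly defines such a child as failed and then scores the child as a responder. The documents do not go that far, because the stricter reading is available but not the only one. What the reply does not remove is that on its reading the word for change does no work in SAP 2.5.1, that Protocol 16.4.3 fits it poorly, that the steroid exemption says nothing about CNIs, and that SAP section 4 does not declare the choice.

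**Conclusion.** The definitions are wrong as written, because they leave two defensible classifications for the same child in the primary endpoint. The gap is narrow: mainly children on a CNI as cGvHD treatment at Cycle 1 Day 1 who respond, flare, are switched and are again in response at the assessment. The number is not given and may be zero. Each such child is about 2.2 points at n = 46. That is the enrolled number, and the full analysis set may be smaller because SAP 2.2 excludes some protocol deviations. The direction is certain: compared with the stricter reading, 5.4.3 can only raise the rate.

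Two stronger inferences should be resisted. One is that a single child could decide whether the trial succeeds. SAP 2.5.2 tests no hypothesis, and the 50% lower limit is used only to plan the sample size, so the comparison of 29/46 with 30/46 shows sensitivity and not a decision rule. The other is that the reported response rate is materially inflated. Any such size comes from assumed multipliers, not from the documents.

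**What to change.** Reconcile SAP 2.5.1, 2.5.3 and 5.4.3 with Protocol 12.4.1 and 16.4.3, so that one stated rule for a CNI switch after a flare applies to response at Cycle 7 Day 1, response at Cycle 4 Day 1 and best overall response. Which rule is right is for the sponsor to settle. If 5.4.3 is intended, declare it in SAP section 4.

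List every CNI switch after Cycle 1 Day 1 from the existing concomitant-medication records, with indication, timing relative to any flare, and reason where recorded. If there are any, report the response rates under both rules as a sensitivity analysis. SAP 2.5 does not repeat the primary analysis for the final report if its data are unchanged, so this should supplement the analysed endpoint and not replace it.

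The cost is a few sentences and a small record review. SAP 5.4.3 relies on route, administration and indication, and the documents show no field for the reason for a switch, so some reasons may not be recoverable. Under the stricter rule the response rate may fall by a child.
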